1.0 Background and Rationale

Alcohol Use Disorders (AUDs) are among the most common and undertreated psychiatric conditions in developed countries¹, contributing to 4% of the global burden of disease². AUDs occur in over 16.6 million adults in the United States alone³. Alcohol consumption has been causally linked to 60 different diseases⁴, and is the leading contributor to premature death and disability among ages 15-49⁵ via associations with injuries, alcoholic liver disease, heart disease and stroke, cancers, and gastrointestinal disease^{2,4}. AUDs also represent an important societal concern, contributing to an estimated economic burden of \$223.5 billion in the United States⁶. With fewer than 10% receiving treatment⁷ and high rates of relapse in those that do,⁸⁻¹¹ there is a clear need for novel and effective therapeutic interventions.

Prevailing views on addiction suggest that altered function of neural reward circuitry is a key mechanism underlying the development of alcohol dependence¹², as abnormal limbic drive may result in increased impulsivity and salience to alcohol related cues^{13,14}. Research has demonstrated that aberrant hyperactivation within fronto-striatal reward (FSR) circuitry is an important biologic correlate of AUD onset, progression, and severity¹³. The medial prefrontal cortex (mPFC) is a central component of the valuation and reward system of the brain¹⁵⁻²². mPFC activation has been associated with saliency and attribution as well as enhanced motivation to use alcohol^{14,23,24}. Research has consistently demonstrated that alcohol cue exposure evokes increased functional activation within the mPFC^{13,25}. Furthermore, this increased activation may predict transition to heavy drinking and is positively correlated with AUD severity²⁶ as well as craving and relapse^{14,25,27-29}. In light of the role that disordered mPFC function plays in AUD, investigators have proposed that this may represent an important target for novel therapeutic interventions. Recent work have demonstrated that transcranial magnetic stimulation (TMS) is a mechanism by which investigators can modulate function of the mPFC and affect AUD relevant phenomenon such as craving³⁰.

Repetitive transcranial magnetic stimulation (rTMS) is a non-invasive neuromodulation technique that received FDA clearance for use in treatment resistant major depressive disorder in 2008 and has become commonly used in clinical practice. rTMS utilizes the application of a repetitively pulsed magnetic field over the scalp to induce an electric field within a discrete area of the cerebral cortex. This electric field results in altered ion flow across the neuronal cellular membrane and ultimately changes in neuronal polarization³¹. rTMS modulates cortical activation depending on the stimulation parameters used^{31,32}. Physiological studies have provided evidence that low-frequency (LF) rTMS, or rTMS delivered at a frequency of 1 Hz or less, produces an inhibitory effect on local cortical excitability. Studies have also demonstrated that LF rTMS can decrease functional connectivity between separate but related cortical structures³³⁻³⁶. Work by our group and others have shown that rTMS is a viable tool for investigating the neural correlates of psychiatric illness as well as a potential therapeutic option for these same conditions^{30,33,37}. Our group has significant experience in rTMS investigations utilizing the treatment paradigm in this protocol, having completed a pilot-study investigating rTMS as a therapeutic in schizophrenia. We are currently conducting

two additional studies of rTMS as a probe of the role that neural circuit aberrations play in cognitive impairment in early-phase psychosis (EPP)³⁷. Additionally, [name], a consultant on this study, is a nationally recognized expert and pioneer in the use of rTMS in studies of substance use disorder. [name] work has focused on rTMS as a probe of frontal-striatal reward (FSR) circuit modulation and its effects on craving^{13,30}. However, though craving is an important phenomenon in substance use disorders, it is neither necessary nor sufficient in treatment of the conditions.

This pilot study intends to address the **critical unmet need** to develop novel treatments for AUD, such as rTMS, that directly impact *drinking behavior*. Binge drinking and high intensity drinking, or consumption meeting *at least* binge criteria, is a high-risk alcohol self-administration (ASA) pattern associated with the binge-intoxication stage of AUD and the rewarding effects of alcohol. We propose to quantify the impact of mPFC rTMS on ASA using our novel "rate-control" paradigm. The rate control paradigm allows subjects to determine how quickly their breath alcohol concentration (BrAC) will change (increase, decrease, or stay the same) over the next 3-5 minute epoch, at the end of which brief computer-assisted assay of craving for alcohol and subjective response attributed to alcohol's effect on stimulation, sedation, liking and well-being in a manner comparable to the Brief BAES^{38,39}. Each assay requires less than 20 seconds to complete and will be administered during the last ~0.5 minutes of alcohol delivery but before selection of the next rate of exposure. The ensemble provides detailed self-administered time course of alcohol exposure and corresponding time-stamped series of quantified perceptions for analysis. This approach has demonstrated sensitivity in associating self-reported high intensity drinking and the time until a binge alcohol exposure of 80 mg/dL (Figure 1).

Our premise is that clinically impactful neuromodulation should change ASA. Coupling rTMS to a laboratory-assessed ASA paradigm could document *causal* changes in drinking behavior attributable to modulation of specific neural circuits. The **goal of this project** is to generate preliminary data supporting our **central hypothesis** - rTMS targeting to the mPFC, a primary cortical input to the FSR circuit, will decrease the rate of alcohol self-administration.

2.0 Objective(s)

Primary Objective

The **primary objective** of this pilot study is to determine the effect size of the relationship between mPFC LF rTMS and a change in the time required to self-administer at least a binge-level alcohol exposure of 80 mg/dL. We hypothesize that,

[figure not shown]

Figure 1: High Intensity Drinking Groups and Time to 80 mg/dL. N=33 subjects completing the rate control ASA paradigm. Groups are defined by multiples of self-reported binge intensity for display. Time to 80 mg/dL is sensitive to drinking intensity ($p = 0.0035$). Report in preparation.

compared to sham stimulation, mPFC LF rTMS will slow the time to a breath alcohol concentration (BrAC) of 80 mg/dL.

Secondary Objective

The **secondary objective** is to explore the effects of mPFC rTMS on subjective responses to alcohol, time until a high intensity drinking exposure, and, during a 4-week follow-up period, self-reported alcohol consumption patterns.

3.0 Outcome Measures/Endpoints

Primary Outcome Measures

The primary outcome measure will be the amount of time subjects take to self-administer enough alcohol to raise their BrAC to 80 mg/dL in the rTMS treatment condition compared to the rTMS sham condition during the two alcohol self-administration sessions.

Secondary Outcome Measures

The secondary outcome measures will be the subjective responses to alcohol during the self-administration sessions and the amount of daily alcohol consumption as measured by Time Line Follow Back (TLFB) during the 4-week follow-up period.

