5.0 Study Design

This will be a single site randomized, 2-session, within-subject cross-over design pilot study (Figure 2). 20 enrolled (of 30 consented) subjects reporting varying levels of binge and high intensity drinking, defined as at least 2 episodes of drinking 4 (for women) or 5 (for men) drinks on an occasion over the last 5 weeks, (unless determined by PI that drinking history meets study objectives), will be enrolled. Subjects will be randomized to undergo one session of rTMS or sham immediately followed by our rate control IV ASA paradigm. Subjects will then return 7-14 days later and undergo the same sequence of events with the opposite intervention (i.e. rTMS or sham) from session 1.

Duration of Treatment

Subjects will complete two stimulation (LF and sham) and IV ASA paradigm sessions over two to three weeks, with one session occurring every 7-14 days. Previous work has demonstrated that a single session of rTMS is sufficient to modulate AUD related behavior³⁰.

Clinical Research Sites

rTMS treatments and alcohol challenge sessions and lab visits will take place at the Indiana Clinical Research Center, in either Goodman Hall at the Neuroscience Center and/or in the Neural Systems Laboratory at Indiana University Hospital.

[name] is the Medical Director of the IU Neurostimulation Program and is a psychiatrist in the IU Department of Psychiatry. [name] and associated research personnel will conduct TMS procedures, help with subject transportation and monitoring, and assist with gathering demographic data. The program has 1 research psychiatrist and 1 research coordinator.

[figure not shown]

Figure 2: Study Design for rTMS Modulation of ASA

[name] is the Research Medical Director of the IU Psychotic Disorders Program (IUPDP). The IUPDP is located in Indianapolis, IN. and is part of the IU Department of Psychiatry. IUPDP research personnel will conduct TMS procedures, help with subject transportation and monitoring, and assist with gathering demographic data. The IUPDP has 2 research psychiatrists, a fully dedicated study manager, a fully dedicated study coordinator, one dedicated subject recruiter, and two raters (1 PhD, 1 Masters level) who have been trained and have extensive experience in conducting the assessments and cognitive tests used as outcome measures.

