6.0 Enrollment/Randomization

Subjects will be recruited through the NSL registry, and self-referrals through advertisement and word-of-mouth. Subjects that meet inclusion/exclusion criteria will be enrolled at the discretion of the Principle investigator and randomly assigned to one of the two schedules (rTMS first, or Sham first).

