7.0 Study Procedures

Recruitment and Screening

Subjects from the NSL registry will be contacted by phone or email, while other subjects will contact the study phone line or email after learning about the study from print, electronic advertising, or word of mouth. Subjects who meet basic criteria will either 1) be invited for an in-person interview when they will consent to participate in the study, or 2) arrange for a remote interview where they will consent to participate and complete interview measures electronically and converse with study staff via IU Zoom Health or similar secure platform. Subjects will complete some or all of the following measures, at the discretion of the principal investigators:

Self-Report Measures:

- The Alcohol Use Disorders Identification Test (AUDIT)
- The Family History of Alcoholism Module of the SSAGA
- The UPPS-P Impulsive Behaviors Scale measures impulsivity traits
- Self-Rating of Effect of Alcohol assessing retrospective sensitivity to the subjective response to alcohol (SRE).
- Short Inventory of Problems – Revised (SIP-r)
- Medical History (including menstrual phase for women)

- Nicotine History Measure
- Penn Alcohol Craving Scale (PACS)
- Subjective Response Questions
- Five Factor Model Form
- Drinking Refusal Self-Efficacy Questionnaire-Revised (DRSEQ-R)
- Alcohol Expectancy Questionnaire (Full and Brief versions)
- Drinking Motives Questionnaire (Full and Brief versions)
- COVID-19 Questionnaire

Interviews:

- The Semi-structured Assessment for the Genetics of Alcoholism – II, Alcohol

Diary Measures:

- Timeline Follow-back (TLFB) modified to assess for one-month recall of alcohol, tobacco, drug, and cannabis use

Screening tools:

- Clinical Institute Withdrawal Assessment for Alcohol Scale (CIWA)
- GAD-7 and GAD-2 Generalized Anxiety Disorder Assessment, 7 and 2 item scales assessing anxiety symptoms over the last 2 weeks
- PHQ-9 and PHQ-2 Patient Health Questionnaire, 9 and 2 item scales assessing depressive symptoms over the last 2 weeks
- Urine pregnancy and drug screen (UPS, UDS, including EtG urine screen at discretion of study physicians)
- Breath Alcohol Concentration Measurement
- Liver function assessment
- TMS Screening Checklist

Miscellaneous:

- Contact Form and Follow-up questionnaires

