Note: Screening tool score above the cutoff or concerning patterns as determined by the study technician may prompt additional testing from the set of measures completed at the interview (For example, PHQ-2 score greater than or equal to the cutoff of 3 will prompt completion of the PHQ-9.).

Subjects that complete part of the interview remotely and appear to meet study criteria will be asked to visit the ICRC for a short visit where they will provide a blood sample, urine, and be paid the interview fee of \$25. Blood samples may be stored indefinitely in a secure location for future genetic research. There is not a plan to submit to the NIH genomic database. At this time, there is no planned analysis for these samples and due to our sample size, we do not meet the requirements for inclusion in the NIH genomic database. Subjects who complete part of the interview remotely and do not meet study criteria will be informed of the decision and mailed a check or gift card in the amount of \$25.

Based on the information collected at the screening interview, the investigators will decide whether or not to enroll the subject in the study. If the subject is enrolled in the

study, they will be either randomly assigned to one of the two schedules, or assigned to one of the two schedules based on group enrollment balance or subject safety at the discretion of the study physicians, and contacted to schedule their experimental sessions. If the subject agrees to enroll in the study and schedules their study visits, they will be sent an email with pertinent information.

Procedures on the testing day

Orientation to Laboratory: On the days of testing, the subject will arrive at the ICRC between 7:00 and 9:00 am and undergo a brief physical exam by ICRC Nurses, testing of urine for hCG in females and a drug screen for all subjects, and documentation of zero BrAC before a 550 cal breakfast is served. *Study protocol will be reviewed and car keys, if the subject drove themselves, taken for safekeeping or confirmed that the keys are held by the hospital valet service.* Age, sex, blood pressure, heart rate, temperature, height, and weight will be measured.

rTMS Treatment

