Subjects approaching the functional exposure limit of 165 mg/dL will have their range of BrAC choices limited in a corresponding way. An alcohol self-administration session may be terminated early at the discretion of the study investigators if the outcome measures have been obtained (for example, the safety limit has been reached and thus binge and high intensity drinking alcohol exposures achieved with corresponding subjective responses). Subject payment will not change and they will not be informed of the reason for early termination to preclude change in behavior at any subsequent sessions.

Except for *ad-libitum* bathroom breaks, participants remain in the testing environment for the duration of the experiment; technician interaction is limited to occasional BrAC samples and dependent-measure data collection.

Upon completion of the infusion and return to the ICRC, participants are served a meal from the ICRC kitchen and remain in a room until at least 7:00 pm, or until BrAC < 35 mg/dL. Subjects may discharge earlier at the discretion of the principal investigator and if transportation has been arranged for them, however subjects are not informed of this

option as it is exercised only in emergencies or urgent situations. If the BrAC is 40 mg/dL or higher at 5:30pm, the participant will be offered a dinner from the ICRC kitchen, *gratis*. Participants will be paid in cash upon discharge from each session, with an escalating payment schedule used to encourage retention. Subjects will be compensated \$25 for the screening interview, \$125 for the first rTMS/Alcohol session, and \$175 for the second rTMS/Alcohol session. Subjects that complete only a portion of any study procedure will be compensated at a rate of \$15 per hour at the discretion of the study physicians.

Alcohol consumption follow-up

Subjects will be contacted and compensated \$25 four weeks after Session 2 for a timeline follow-back assessment of drinking⁴⁹.

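### The 4-week TLFB drinking outcome starts after every completer has had both rTMS and sham and names no contrast; a fixed 7-day window after Session 1 would add an exploratory rTMS-versus-sham estimate

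*Combined protocol and SAP*

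**What the plan says.** Section 2.0 sets out to explore what mPFC rTMS does to, among other things, "during a 4-week follow-up period, self-reported alcohol consumption patterns". Section 3.0 names the matching outcome as "the amount of daily alcohol consumption as measured by Time Line Follow Back (TLFB) during the 4-week follow-up period". Section 7.0 (Alcohol consumption follow-up) times the contact at "four weeks after Session 2 for a timeline follow-back assessment of drinking".

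The design is a two-session crossover. Section 5.0: "Subjects will then return 7-14 days later" and "undergo the same sequence of events with the opposite intervention (i.e. rTMS or sham) from session 1".

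Section 3.0 states an rTMS-versus-sham comparison for the primary outcome and none for TLFB. The only analysis in Section 12.0 is a Cox model for laboratory self-administration.

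The calendar in Section 9.0 marks TLFB at the interview, both experimental visits and follow-up. The instrument is described as "modified to assess for one-month recall of alcohol, tobacco, drug, and cannabis use", but only in the list of screening measures in Section 7.0.

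On allocation, Section 6.0 and the rTMS Treatment text of Section 7.0 describe random assignment to sequence. The Recruitment and Screening text of Section 7.0 also lets a subject be "assigned to one of the two schedules based on group enrollment balance or subject safety at the discretion of the study physicians".

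**The concern.** The objective asks about an effect of rTMS, yet the window opens when no completer is left with only one condition. Three summaries are possible, and the plan does not choose among them:

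- **Pooled 4-week mean.** It has no comparator.
- **Change from before the sessions.** It mixes rTMS with sham, two IV alcohol sessions, and regression to the mean, since subjects are selected on recent binge drinking (Section 4.0, inclusion criterion 5).
- **Comparison by sequence.** It is protected by randomisation where that was used, but both groups have had rTMS and differ only in how long ago.

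The days between the two sessions are the only period in which one group has had rTMS alone and the other sham alone. They are not named as an outcome. The pilot exists to supply effect sizes for a later study, and its one measure of drinking outside the laboratory would supply a heavily diluted one, or one that cannot be attributed.

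**Working it through.** **The plan's own figure.** 20 enrolled × (1 − 0.30) = 14 completers, as stated in Section 12.0. With equal sequences (assumed) that is 7 v 7. The plan gives no SD, effect size or power for TLFB, so there is nothing further to reproduce.

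**Share of the effect kept.** Assume a constant daily effect lasting L days and a gap of g days between sessions (7 to 14, Section 5.0).

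- 28-day mean after Session 2, by sequence: [min(L, 28) − min(max(L − g, 0), 28)] / 28
- Fixed 7 days from Session 1: min(L, 7) / 7

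| L (days) | 28-day, g = 7 | 28-day, g = 14 | 7-day after Session 1 |
|---|---|---|---|
| 1 | 4% | 4% | 14% |
| 3 | 11% | 11% | 43% |
| 7 | 25% | 25% | 100% |
| 14 | 25% | 50% | 100% |
| 28 | 25% | 50% | 100% |
| 42 | 0% | 0% | 100% |

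The 28-day maximum over L is g/28: 25%, 36% and 50% for g = 7, 10 and 14. It reaches zero once L ≥ 28 + g.

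**A different decay shape.** With exponential decay and a half-life of 1 to 28 days, the 28-day contrast keeps about 5% to 27% of the initial effect (0% if permanent). The 7-day window keeps about 20% to 92% (100% if permanent). The direction is the same.

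**Offset for noise.** A 7-day mean is noisier than a 28-day mean. With day-level intraclass correlation ICC, the SD ratio is sqrt{[ICC + (1 − ICC)/7] / [ICC + (1 − ICC)/28]}: 2.00 at ICC 0 and 1.05 at ICC 0.5 (assumed range). The signal ratio is 4 for g = 7 (L up to 28) and for g = 14 with L up to 7. It falls to 2 for g = 14 with L from 14 to 28. Dividing gives the standardised advantage:

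- ratio 4: 4/2.00 = 2.0 to 4/1.05 = 3.8
- ratio 2: 2/2.00 = 1.0 to 2/1.05 = 1.9

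So with 14-day gaps, long effects and little day-to-day correlation, the gain disappears.

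**Precision.** Unadjusted half-width = t(0.975, 12 df) × sqrt(2/7) = 2.179 × 0.5345 = 1.16 SD at 7 v 7. If all 20 supplied the window (10 v 10), it is 0.94 SD. Adjustment for earlier drinking should narrow this by an amount the documents cannot fix: ICC 0 to 0.5 implies a correlation between a 28-day baseline mean and the 7-day mean of anywhere from 0 to 0.92.

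**Within-subject alternative.** For the 7 days after each session, 14 completers and within-subject correlation ρ, half-width = 2.179 × sqrt[2(1 − ρ)/14]: 0.69, 0.58 and 0.45 SD at ρ = 0.3, 0.5 and 0.7 (assumed). It is tighter but assumes no carryover; under the constant-effect model its share falls to 50% once L reaches g + 7.

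**Why a fixed 7 days.** The shortest gap is 7 days, so a window starting on the Session 1 evening always ends before Session 2 and contains each weekday once. For sessions starting Monday to Friday (assumed), a window that followed the actual gap would hold 2 to 4 Friday/Saturday days at gaps of 9, 10 or 11 days.

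**The case against.** **This is an exploratory item in a pilot about laboratory self-administration, and no secondary outcome is given an analysis.** True, and it caps the severity. TLFB still differs from the subjective responses: those are collected in each session, so their rTMS-versus-sham contrast is built in. The TLFB window has none.

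**The data are already planned.** Largely so. TLFB is scheduled at Visit 2, and one-month recall would cover a 7-14 day gap. But that recall length appears only in the screening list, so the documents do not establish that the Visit 2 TLFB reaches back to Session 1, and the interval is not named as an outcome. This objection shows mainly that the change is cheap.

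**The replacement is too imprecise.** This stands as a reason not to test. It does not stand against reporting an estimate with its interval.

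**A by-sequence contrast already exists.** This also stands. A reader might infer that the 4-week outcome can yield no rTMS-versus-sham information at all. The documents do not support that: where sequence was randomised, the 28-day comparison is valid, though diluted and not named.

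**The shortened first evening is harmless.** A reader might infer that it affects both sequences alike, since everyone stays until evening. The documents do not support that either. Release on a session day also depends on BrAC (Section 7.0), hence on the amount infused, which the primary hypothesis expects to differ by condition.

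**Conclusion.** The concern holds as a minor point. The only named drinking outcome starts after both conditions, and no contrast or analysis is stated for it. The best contrast available in that window keeps at most 25% to 50% of a constant effect, depending on the gap, and nothing once the effect outlasts the follow-up. A 7-day window after Session 1 keeps 100% of an effect lasting a week or more, but only 14% of a one-day effect.

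The missing contrast is read directly from the text. The size of the gain rests on assumptions about effect duration, decay shape and day-to-day correlation, none of which the documents give, and in the least favourable case it is nil. The primary outcome is not affected.

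**What to change.** Add one exploratory rTMS-versus-sham drinking outcome: mean drinks per day over a fixed 7 days from the evening of Session 1, infused alcohol excluded. Take it from the Visit 2 TLFB, completed before stimulation, and state that this TLFB reaches back to Session 1. Then specify:

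- **Estimate.** Difference by assigned sequence with a 95% CI and no test, adjusted for the TLFB before Session 1 (Visit 1, or screening if Visit 1 is missing).
- **Sensitivity 1.** Exclude subjects whose sequence was assigned at discretion.
- **Sensitivity 2.** Drop the Session 1 evening, because discharge time and residual BrAC may differ by condition. This leaves six days and omits the session's own weekday.
- **Missing data.** State that subjects without a Visit 2 TLFB are not in this estimate, and report their number by sequence.
- **Optional companion.** A within-subject contrast with the same 7 days after Session 2, with a period term and the no-carryover assumption stated.
- **4-week TLFB.** Report it descriptively, overall and by sequence, without attributing it to rTMS.

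The cost is the outcome wording, a short analysis paragraph and one sentence on recall. No visit is added; if the Visit 2 TLFB was meant to be shorter, it needs a few more recall days. The remaining drawbacks are a wide interval, a gain that may vanish with 14-day gaps and long effects, and little sensitivity to an effect of about a day.
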